3 STUDY OBJECTIVES

The primary efficacy and safety objectives of this study are:

Efficacy:

• To evaluate the reduction in liver fat content, as assessed by magnetic resonance imaging proton density fat fraction (MRI-PDFF), from baseline to Day 61 in subjects with elevated BMI treated with HU6 compared to placebo.

Safety:

• To evaluate safety and tolerability of 61 days of repeated daily dosing of HU6 in overweight and obese subjects as defined by BMI.

The secondary objectives of this study are:

- To assess the rate and amount of body weight loss after 61 days of HU6 treatment.
- To assess change from baseline in whole body adiposity by MRI after 61 days of HU6 treatment.
- To characterize the pharmacokinetic (PK) profile of HU6 and its metabolites, DNP and M1, over 61 days of dosing in subjects with high BMI.
- To evaluate and correlate changes from baseline in measures of liver composition with changes in liver fat content after dosing with HU6.
- To investigate the pharmacodynamic (PD) effects of HU6 on metabolic and cardiovascular risk factors.
- To investigate the PD effects of HU6 on metabolomic, proteomic, and lipidomic profiles.
- To characterize the dose/exposure relationships of the efficacy and PD effects of HU6, as data allow

4 STUDY ENDPOINTS

4.1 Primary Endpoint

• Relative change from baseline in liver fat content, as assessed by MRI-PDFF at Day 61.

4.2 Secondary Endpoints

Pharmacodynamics

• Change from baseline in body weight at Day 61.

- Change from baseline in whole body adiposity at Day 61 [i.e., total visceral adipose tissue (VAT) and subcutaneous adipose tissue (SAT)]
- Changes from baseline in surrogate measures of liver inflammation and fibrosis at Day 61: Fibroscan® Vibration-controlled Transient Elastography (VCTE), Fibroscan® Controlled Attenuation Parameter (CAP) score, and Enhanced Liver Fibrosis (ELF) score.
- Change from baseline in lipid parameters and cardiovascular risk biomarkers at Day 61: serum high sensitivity C-reactive protein (hs-CRP), Lp(A), Apo B, low-density lipoprotein (LDL), high-density lipoprotein (HDL), total cholesterol, triglycerides, and free fatty acids (FFA).
- Change from baseline in metabolic disease parameters at Day 61: homeostatic model assessment for insulin resistance (HOMA-IR), fasting blood glucose concentrations, glycated albumin concentrations, HbA_{1c}.

Safety and Tolerability

- Summary of physical examinations findings over the course of the study.
- Adverse event (AE) assessment over the course of the study.
- Assessment of vital sign parameters over the course of the study, including resting systolic and diastolic blood pressure, resting heart rate, resting respiratory rate, and oral body temperature.
- Assessment of body weight over the course of the study.
- Safety 12-lead electrocardiograms (ECGs) over the course of the study.
- Assessment of clinical laboratory values (hematology, full biochemistry panel (including lipid panel, creatinine phosphokinase (CPK), magnesium, liver function tests, and urinalysis over 61 days of dosing.
- Assessment of ophthalmologic examination, including slit lamp, prior to and after 61 days of dosing.

Pharmacokinetics

- Population PK analysis of HU6 parent and metabolites, DNP and M1. The following PK parameters will be estimated as appropriate: maximum observed plasma drug concentration (C_{max}), time to peak plasma concentration (T_{max}), apparent terminal half-life ($t_{1/2}$), delay between the time of dosing and time of appearance of concentration in the sampling compartment (T_{lag}), area under the concentration-time curve from time zero to the time of the last measurable concentration (AUC_t), area under the concentration-time curve from time zero to infinity (AUC_{inf}), apparent oral clearance (CL/F), apparent volume of distribution (V_z/F), apparent terminal elimination rate constant (λ_z). Other PK parameters may be calculated, as data allow and as appropriate.
- As data permit, noncompartmental analysis of HU6 parent and metabolites, DNP and M1. The following PK parameters will be calculated: C_{max}, AUC, and accumulation.

• Modeling of exposure response relationships of HU6, DNP, and M1 and efficacy/pharmacodynamic endpoints, as appropriate.

4.3 Exploratory Endpoints

- Change from baseline in metabolomic and lipidomic profiles (One Way Liver-[OWL] metabolomic and lipidomic assays) at Day 61.
- Change from baseline in proteomic profiles (SomaScan®) at Day 61.
- Change from baseline in serum alanine aminotransferase (ALT) and aspartate aminotransferase (AST) concentrations at Day 61, as data allow.

5 GENERAL METHODS

5.1 Analysis Populations

The analysis populations will be as follows:

Intent-to-Treat (ITT): includes all randomized subjects. Subjects will be analyzed according to treatment as randomized.

Full Analysis Set (FAS): includes all randomized subjects who receive at least 1 dose of treatment and have <= 10 pounds of weight gain or weight lost from screening visit to Day 1. Subjects will be analyzed according to treatment as randomized.

Safety: includes all randomized subjects who receive at least 1 dose of treatment. Subjects will be analyzed according to treatment as received.

The PK concentration population and the PK parameter population will be defined in the PK analysis plan.

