5.4 Study Duration

For an individual subject, the study will last approximately 120 days (up to 45 days for screening, 61 days of dosing, up to 14 days for final visit after dosing completion.

The entire study is estimated to last approximately 5 months: first subject in May 2021 with last subject anticipated being completed in September 2021.

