12.3 Data Analysis

12.3.1 Analysis Populations

Intent-to-Treat (ITT): includes all randomized subjects.

Full Analysis Set (FAS): includes all randomized subjects who receive at least 1 dose of treatment.

PK Concentration Population: includes all subjects who receive at least one dose of HU6 and have at least one adequately documented plasma sample obtained and analyzed for measurable HU6, DNP and M1 concentrations.

PK Parameter Population: includes all subjects who have an evaluable HU6, DNP and M1 plasma concentration data.

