12.3.2 Efficacy Analysis

The primary efficacy endpoint is the reduction in liver fat content measured by the relative change from baseline, as assessed by MRI-PDFF at Day 61. The hypothesis of interest are 2-sided tests comparing each active HU6 treatment groups to the placebo.

 $\begin{aligned} H_{01}: \mu_{placebo} &= \mu_{HU6\ 170mg} \text{vs} \ H_{11}: \mu_{placebo} \neq \mu_{HU6\ 170mg} \\ H_{02}: \mu_{placebo} &= \mu_{HU6\ 340mg} \text{vs} \ H_{12}: \mu_{placebo} \neq \mu_{HU6\ 340mg} \end{aligned}$

 $H_{03}: \mu_{placebo} = \mu_{HU6\ 510mg} \text{vs}\ H_{13}: \mu_{placebo} \neq \mu_{HU6\ 510mg}$

Relative change from baseline in liver fat content, will be analyzed for the FAS using an analysis of variance (ANCOVA) model, including treatment group, HbA_{1c} stratification (normal range versus between 5.7% and 9.0% inclusive) and baseline liver fat from MRI-PDFF as fixed effects. This estimand will include available MRI-PDFF evaluations that occur before discontinuation of treatment. The differences between treatment groups will be based on the least square mean (LSMean) differences between each HU6 group and placebo. A separate comparison of the combined HU6 groups and placebo may be conducted. The corresponding 95% confidence interval (CI) will be presented.

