11 EFFICACY ANALYSES

The primary efficacy endpoint will be the reduction in liver fat content measured by the relative change from baseline, as assessed by MRI-PDFF at Day 61. The hypotheses of interest are 2-sided tests comparing each active HU6 treatment group to the placebo group.

```
\begin{split} H_{01} \colon & \mu_{placebo} = \mu_{HU6 \; 150mg} \text{vs} \; H_{11} \colon \mu_{placebo} \neq \mu_{HU6 \; 150mg} \\ & H_{02} \colon \mu_{placebo} = \mu_{HU6 \; 300mg} \text{vs} \; H_{12} \colon \mu_{placebo} \neq \mu_{HU6 \; 300mg} \\ & H_{03} \colon \mu_{placebo} = \mu_{HU6 \; 450mg} \text{vs} \; H_{13} \colon \mu_{placebo} \neq \mu_{HU6 \; 450mg} \end{split}
```

Summary statistics (n, mean, standard deviation, minimum, median, and maximum) will be presented for the observed values for MRI-PDFF at each time point for the FAS population, as described in Section 5.2, Summarization of Data. Summary statistics will also be presented for the change-from-baseline values to each postbaseline time point as well as placebo-corrected change-from-baseline values to each postbaseline time point. In these displays, baseline will be defined as the last non-missing value prior to first dose of study medication. Figures will be generated appropriate to the data output.

Mean change from baseline in liver fat content will be analyzed for the FAS population using an analysis of covariance (ANCOVA) model, including treatment group, HbA_{1c} stratification (normal range versus between 5.7% and 9.0% inclusive) and baseline liver fat from MRI-PDFF as fixed effects. This estimand will include available MRI-PDFF evaluations that occur before discontinuation of treatment. The difference in LS Means for the change from baseline, corresponding 95% CIs, and P values will be provided to assess the treatment differences between placebo and each HU6 treatment group. A separate comparison of the combined HU6 groups and placebo may be conducted.

Responder status (n, %) at Day 61 will be presented. A subject will be deemed a responder if their MRI-PDFF showed a 30% or more reduction from baseline at Day 61. Additional exploratory analysis may be performed such as a different threshold then the 30% or more reduction from baseline due to the short duration of the study.

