12 PHARMACODYNAMICS ANALYSES

For each pharmacodynamic variable, summary statistics (n, mean, standard deviation, minimum, median, and maximum) will be presented for the observed values at each time point for the FAS population, as described in Section 5.2, Summarization of Data. Summary statistics will also be presented for the change-from-baseline values to each postbaseline time point. For glycated albumin, placebo-corrected change-from-baseline values to each postbaseline time point will be presented. In these displays, baseline will be defined as the last non-missing value prior to first dose of study medication. Figures will be generated appropriate to the data output.

For pharmacodynamic variables with only a Day 61 post-baseline assessment [i.e., ELF variables, HbA_{1c}, abdominal MRI [liver volume, VAT, and SAT], and Fibroscan [Steatosis/VCTE and Fibrosis/CAP], summary statistics will be presented for the change-from-baseline values for each variable at Day 61. Placebo-corrected change-from-baseline values at Day 61 will be presented for abdominal MRI [liver volume, total visceral adipose tissue (VAT) and subcutaneous adipose tissue (SAT)], and Fibrosis/CAP. The ELF variables will be ELF score, hyaluronic acid, procollagen III amino-terminal peptide (PIIINP), and tissue inhibitor of matrix metalloproteinase 1 (TIMP-1). Figures will be generated appropriate to the data output.

For each pharmacodynamic variable with only a Day 61 post-baseline assessment, mean change from baseline will be analyzed for the FAS population using an ANCOVA model, including treatment group, HbA_{1c} stratification (normal range versus between 5.7% and 9.0% inclusive) and the baseline score of the response variable as fixed effects. The difference in LS Means for the change from baseline, corresponding 95% CIs, and P values will be provided to assess the treatment differences between placebo and each HU6 treatment group.

For the abdominal MRI liver volume and adiposity, the above summary statistics, an ANCOVA model including treatment group and the baseline score of the response variable as fixed effects, and the responder status will also be presented for the subjects randomized only to the HbA1c between 5.7% and 9.0% subgroup.

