Continuous pharmacodynamic endpoints with repeated post-baseline assessments [changes from baseline in ApoB, Lp(a), glycated albumin, hs-CRP, liver panel parameters (total cholesterol, HDL, calculated LDL, VLDL, triglycerides, and FFA), HOMA-IR Calc (i.e., the average of the 3 blood draws 5 minutes apart at each scheduled visit), body weight (via InBody Scale), and fasting blood glucose] will be analyzed for the FAS population using a mixed model for repeated measures (MMRM). The estimand will include available post-baseline response data that occur before discontinuation of treatment. The baseline score will be included as the covariate, and HbA_{1c} stratification, treatment group, visit, and the interaction between treatment group and visit will be estimated based on the LSMeans from the MMRM.

For body weight, a responder status (n, %) at Day 61 will be presented. A subject will be deemed a responder if their body weight showed a 1% or more reduction from baseline at Day 61. Additional exploratory analysis may be performed.

In addition, for body weight, the above summary statistics, an MMSE analysis and the responder status will also be presented for the subjects randomized only to the HbA1c between 5.7% and 9.0% subgroup. For the MMRM, the baseline score will be included as the covariate, and treatment group, visit, and the interaction between treatment group and visit will be estimated based on the LSMeans from the MMRM.

All pharmacodynamic results will be displayed in subject listings.

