18 REVISIONS TO STATISTICAL ANALYSIS PLAN

Date	Revision
03 September 2021	The SAP was revised to analyze the HOMA-IR Calc only (i.e., the average of the 3 blood draws 5 minutes apart at each scheduled visit). Insulin, glucose, and C-peptide results will be listed only.
02 December 2021	Added summary statistics for placebo-corrected change-from-baseline values to each postbaseline time point for specified parameters and figures will be generated appropriate to the data output. Added responder status summary statistics for specified parameters at Day 61.
09 December 2021	For subjects in HbA1c 5.7% - 9.0% subgroup only, added summary statistics for change-from-baseline values to each postbaseline time point for specified parameters, placebo-corrected change-from-baseline values to each postbaseline time point for specified parameters, and MMRM or ANCOVA analysis as appropriate. Figures will be generated appropriate to the data output. In addition, added responder status summary statistics for specified parameters at Day 61. An addition, a criterion on body weight was added to the definition of Full Analysis Set (FAS).

16

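### The SAP narrows the protocol's Full Analysis Set with a late, unexplained 10-pound weight rule, and no efficacy model is kept on the protocol's population

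*SAP*

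**What the plan says.** Protocol 12.3.1 reads: "Full Analysis Set (FAS): includes all randomized subjects who receive at least 1 dose of treatment". It sets no condition on weight. Protocol 12.3.2 says that the primary endpoint "will be analyzed for the FAS using an analysis of variance (ANCOVA) model", and Protocol 12.3.3 assigns the pharmacodynamic MMRM to the same set.

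SAP 5.1 uses the same name for a smaller group. Besides one dose, a subject must "have <= 10 pounds of weight gain or weight lost from screening visit to Day 1". SAP 11 states: "Mean change from baseline in liver fat content will be analyzed for the FAS population using an analysis of covariance (ANCOVA) model". SAP 12 says that for variables measured after baseline only at Day 61, "mean change from baseline will be analyzed for the FAS population using an ANCOVA model", and it also puts the repeated-measures pharmacodynamic endpoints on the FAS.

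The revision table in SAP 18 places the weight criterion in its last entry, 09 December 2021. It says only that such a criterion was added. The entries of 03 September and 02 December 2021 do not mention it.

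**The concern.** These are two current texts that define the primary population differently under one name. A reader who takes FAS in its protocol sense will misread which subjects the primary result describes.

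Protocol 12.1 leaves further statistical detail to the SAP, but changing the primary analysis population is more than a detail. With about 20 subjects per arm, a few exclusions can move an arm mean. When the exclusion rule is written late and without a reason, the documents cannot show that it was chosen independently of the data. Protocol 6.6 keeps treatment codes from sponsor data-management and analysis staff while the trial runs. It does not say whether that still held on 09 December 2021.

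**Working it through.** **1. Definitions and uses side by side**

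| Set | Membership | Use |
|---|---|---|
| Protocol FAS (12.3.1) | Randomized, at least one dose | Primary ANCOVA, PD MMRM (12.3.2, 12.3.3) |
| SAP FAS (5.1) | Same, and weight change of 10 lb or less from screening to Day 1 | Primary ANCOVA, Day-61-only PD ANCOVAs, PD MMRMs (11, 12) |
| SAP ITT (5.1) | All randomized | Disposition only (6) |
| SAP Safety (5.1) | Same membership as protocol FAS, analyzed as received | Demographics, safety, descriptive InBody summaries and responder counts |

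No ANCOVA or MMRM is assigned to the protocol FAS or to ITT. The models for the HbA1c 5.7% to 9.0% subgroup name no population of their own and follow from the FAS analyses, so they do not fill the gap.

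**2. Timing**

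Protocol 5.4 plans for "first subject in May 2021 with last subject anticipated being completed in September 2021". From 30 September to 09 December 2021 is 31 + 30 + 9 = 70 days. This counts from a planned month. The actual last visit, database lock and unblinding dates are not in the documents.

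**3. Does the rule follow from eligibility?**

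Exclusion criterion 4 is a percentage: more than 5% in the 3 months before the study. Ten pounds equals 5% at 200 lb (10/200) and is less than 5% above that weight. As an illustration, an 11-lb change at 240 lb is 11/240 = 4.6%. That is inside the 5% limit but outside the SAP FAS. The SAP rule is therefore not a restatement of the eligibility criterion.

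**4. The plan's own power figure**

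Inputs (Protocol 12.2, SAP 5.3): difference 30, SD 30, two-sided alpha 0.05, 17 per group, 15% dropout.

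- Enrolment: 68/(1 − 0.15) = 80. This reproduces.
- Two-sample t-test: noncentrality = 30/(30 × √(2/17)) = 2.915, df = 32, power 80.7%. This agrees with the stated figure of at least 80% and leaves a margin of less than 1 point.

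**5. If the rule removes evaluable subjects**

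The number removed is not given, so this is an assumed range. The planned model has four arm means, one stratum term and one baseline slope, so error df = 4n − 6. Noncentrality is 30/(s × √(2/n)). The residual SD s is 30 with no covariate gain, or 30 × √(1 − 0.3²) = 28.6 if the baseline–outcome correlation is assumed to be 0.3.

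| Evaluable per arm | Two-sample t-test | ANCOVA, no covariate gain | ANCOVA, assumed r = 0.3 |
|---|---|---|---|
| 20 | 86.9% | 87.7% | – |
| 17 | 80.7% | 81.9% | 85.3% |
| 16 | 78.1% | 79.4% | 83.0% |
| 15 | 75.3% | 76.7% | 80.5% |

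One subject fewer per arm costs about 2 to 3 points. The sample-size text allows for dropout but not for this exclusion.

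**The case against.** The strongest reply is that the rule is harmless and sensible.

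- **Pre-dose weights.** Both weights come before the first dose, so the comparison by randomized arm is kept. This stands, and no claim is made that treatment drives the exclusions.
- **Small effect.** If exclusion is unrelated to outcome, dropping 1, 2 or 3 of 17 subjects shifts an arm mean with an SD of 30 × √(1/(17 − k) − 1/17), about 1.8, 2.7 or 3.4 points. The standard error of the treatment difference is 30 × √(2/17) = 10.3 and the planned effect is 30. This also stands. It limits the size of the problem but does not settle which population is primary.
- **Plausible rationale.** The protocol wants weight-stable subjects (exclusion criteria 4 and 5, and Section 8.3.3). The baseline MRI may be up to 30 days old at Day 1, so a large weight change could make it unrepresentative. That may be the reason, but the SAP does not say so, and it would support a sensitivity set equally well.
- **Lateness is unproven.** The 70 days run from an estimate, and Protocol 12.1 lets enrolment be extended. It is right that a change after unblinding cannot be asserted. Equally, the documents do not show that the change was made blind.
- **Disclosure and exploratory status.** The rule is visible in SAP 5.1, set sizes are tabulated under SAP 6, and the study calls itself exploratory. It still names a primary endpoint and three two-sided tests at 0.05. Listing the data does not supply the missing analysis.

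Running the models on the protocol FAS only as a sensitivity analysis would remove part of the concern. It would leave the two documents in conflict on the primary population.

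**Conclusion.** The concern holds. The protocol and the SAP contradict each other on the primary analysis population. The SAP's version carries a late date and no reason, and the SAP assigns no efficacy model to the protocol's population. This needs to be fixed.

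The numerical effect is conditional and probably small. It is zero if the rule removed nobody, or only subjects with no usable Day 61 scan. At the planned 17 evaluable per arm, losing one or two per arm takes ANCOVA power from 81.9% to 79.4% or 76.7% with no covariate gain. With the assumed correlation of 0.3 it stays above 80%. These figures rest on the plan's difference and SD of 30 and on equal losses across arms. The documents do not show which way, if at all, the treatment estimates would move. No finding is made that the change followed unblinding.

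**What to change.** - In SAP 5.1, return the FAS to the protocol definition: every randomized subject with at least one dose, analyzed by assigned arm, with no weight condition.
- Run the primary ANCOVA and the pharmacodynamic ANCOVA and MMRM models on that set.
- Define the 10-pound subset under its own name, for example a weight-stable set, and repeat the same models on it as a labelled sensitivity analysis.
- In SAP 18, give the reason for the 10-pound rule and state whether those who wrote it had access to treatment codes at the time.

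The cost is SAP wording and one rerun of each model. No new data are needed. SAP 6 already tabulates the size of each set, so no extra count table is required.

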5.2 Summarization of Data

Study results will be summarized by treatment group (i.e., 150 mg QD, 300 mg QD, 450 mg QD, and Placebo) in tabular format with descriptive statistics and/or in subject listings.

For placebo-corrected results, at each visit, the average placebo mean change from baseline will be subtracted from each subject's mean change from baseline.

Statistical testing will be 2-sided and performed using a significance (alpha) level of 0.05. There will be no adjustment for multiple comparisons for this exploratory study.

No imputation of missing data will be performed. No windowing of visits will be performed unless otherwise specified.

5.3 Sample Size Justification

A sample size of 17 subjects per group provides at least 80% power to detect a 30% difference in the mean relative change from baseline in liver fat content at Day 61, when the standard deviation is 30% [PASS 2020: Two sample t-test, alpha=.05]. Assuming a 15% dropout rate, up

to 80 subjects should be enrolled to ensure that at least 68 subjects, 17 per group, are evaluable for the primary efficacy endpoint analysis.

5.4 Output Production and Validation

All analyses will be performed using SAS V 9.3 or higher (SAS Institute, Inc, Cary, North Carolina, USA). Validation and quality control of the tables and listings, which display the results of the statistical analysis of the data from this study, will follow the appropriate Innovative Analytics standard operating procedures (SOPs).

